##### Secondary outcomes

Secondary outcomes include the Bayley-III language, motor, and socioemotional subscales and the binary outcomes of whether patients complete EI referrals and services at 12 months. Descriptive statistics for demographic, behavioral, and environmental characteristics measured at baseline will be examined across the two treatment groups to assess the success of the randomization. The secondary outcomes can be modeled using either a linear or logistics mixed effects model, which has similar flexibility. As a secondary analysis, we will examine differences in dosage (duration of EI service use and number of EI service visits) between intervention groups among those eligible for services. We will also examine the impact of public policy changes on the proportion eligible for EI and on the number of service visits pre- and post-change. In addition, we will examine the effects of the intervention by race/ethnicity group, sex, and age group (<18 months, >18 months) to assess for differential intervention effects.

---

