### **6.5 Sample Size, Statistical Power and Analysis Plan**

Our target sample size accounting for clustering by practice site for patients with complete 12-month follow-up is 300 participants. Assuming at least an 80% follow-up rate, the number needed to recruit to obtain this final sample size is about 360. Since a partial goal of the proposed intervention is to increase patient engagement, the rate of drop out is likely to be lower among the intervention group. If we conservatively assume that the drop-out rate among control patients is double that of patients on the intervention, the sample of patients

with complete follow-up will consist of approximately 130 control patients and 170 intervention patients.

Using the Bayley-III cognitive subscale as a primary outcome, we assert that the proposed intervention would be successful if it resulted in an increase of 3 points or more on this subscale. This is the minimal clinically significant outcome difference. Thus, based on the proposed sample size, we would obtain 96% power to detect a clinically meaningful difference in the Bayley-III cognitive scores. The power was estimated based on a simulation study that assumed that the sole impact of the intervention was on increasing enrollment into EI. Based on expected cognitive improvements due to EI found by Guralnick et al, we further assume that children who enrolled in EI had an average increase over a 12 month period of 10 points on the cognitive scale with a standard deviation of 1 point compared to patients who did not enroll. Based on these assumptions, an increase of 3 points on the cognitive scale between the intervention and control group would be the result of an increased rate of enrollment from 50% among controls to 80% among the intervention group. These rates of enrollment are consistent with rates suggested by our pilot data (Preliminary Studies Section).

**Figure 1** *Assessment of power to detect a clinically meaningful difference*

Power	n	
0.96	300	Assuming a minimal clinically significant outcome difference ( $\geq 3$ points increase in the BSID-III cognitive subscale)

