## 7 STUDY INTERVENTION

### 7.1 Main RCT

#### 7.1.1 Description

With the implementation of the intervention, a modified FN model, the FNs will partner with families, engage them in the early intervention program, and provide ongoing communication with families, clinicians, and EI staff. Using data captured in the medical record, the FN will either meet with or speak with families remotely at the beginning of the study to review results of developmental screening tests and/or milestone assessments. This modified FN model process proceeds in five modules. Specifically, they will provide to families 1) education regarding knowledge of early child development, 2) information on the EI system and steps necessary to complete an EI referral, 3) brief motivation interviewing to assess families' goals and treatment preferences and level of interest in initiating EI referrals, 4) ongoing assistance to overcome barriers to completing EI referrals and maintaining EI enrollment, and 5) social work referrals in the event of family crisis or medical complexity. Specific procedures in separate modules, e.g. Early Intervention Intake Monitoring, have been manualized. The FN will contact families weekly to monthly by phone, text messaging, or email depending on family preference to monitor initiation and completion of referral steps, identify family concerns and/or barriers to referral completion, and assist families with problem-solving to identify barriers and solutions to complete EI referrals. Using email or telephone, the FN will also communicate with pediatric clinicians and EI staff to clarify treatment plans and goals and address emerging issues. A fidelity checklist developed in the pilot study will be utilized to assess self-reported task completion by the FN (0- not completed, 1- partially completed, 2- fully completed). In addition, the FN will summarize patient encounters, e.g. telephone calls with parents, in a log file. In the control arm, eligible children and their families will follow usual care procedures. As such, families are counseled by their clinicians, provided with educational handouts on development and the EI process, and referred to EI using electronic faxes from the clinic offices to the EI administrative office. EI staff then contact families by phone to initiate the EI referral process and arrange visits to complete the intake and evaluation (see Fig. 3). Families that fail to complete EI referrals and/or services in a timely manner may be dropped by EI but can be re-referred by their clinicians to complete the process later.

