Analysis: Test the association between study arm at 3 months and EI referral completion and the association between EI parent engagement at 3 months (mediator) and EI referral completion. If both associations are significant, complete a mediation analysis of the association between study arm and completion of EI referrals, mediated by parent EI engagement.

- b. *Hypothesis 2b:* Completion of EI referrals and participation in EI services (dosage) will mediate the association between program participation (duration), parent engagement, and child developmental status

Analysis of EI referral completion and child development status: Test the association between EI engagement at 3 months and Bayley language & cognitive T scores and the association between MDE completion (mediator) and EI engagement at 3 months. If both associations are significant, complete a mediation analysis of the association between EI engagement at 3 months and Bayley language and cognitive T scores, mediated by EI referral completion.

Analysis of program participation and child development scores: Test the association between program participation and Bayley language & cognitive T scores and the association between referral completion (mediator) and program participation. If both associations are significant,

ODEI Study Statistical Analyses Plan

complete a mediation analysis of the association between program duration and Bayley language and cognitive T scores, mediated by referral completion.

Variable Definitions:

- Program participation: participation in ODEI intervention
- Completion of EI Referrals: Completion of Multidisciplinary Evaluation (MDE)
- Initiating EI services: Date of first early intervention service
- Duration of EI services: The time between the EI service initiation and discharge from early intervention OR 12 months from randomization (if discharge date is unavailable)
- Developmental outcomes: Language and cognitive composite scores from BSID III assessment.
- Parent engagement: total score from 2 subscales on parent engagement (Buy-In/Receptivity to EI and Advocacy/Navigating the EI Process)

Aim 3: To explore whether the home learning environment, parental health literacy, or poverty moderate the effects of the Opening Doors to Early Intervention Program on child developmental status.

a. *Aim 3a:* To explore whether differences in developmental scores between intervention and control groups varies by the richness of home learning environment

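### SAP Hypothesis 2b names participation in EI services as a second mediator, but no planned analysis tests it, so part of an effect running through services could be reported as direct

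*SAP*

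**What the plan says.** Hypothesis 2b in the SAP reads: "Completion of EI referrals and participation in EI services (dosage) will mediate the association between program participation (duration), parent engagement, and child developmental status". Referral completion and service participation are both mediators in that sentence.

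Two analyses follow.

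- The first takes parent engagement as the exposure. It tests "the association between MDE completion (mediator) and EI engagement at 3 months" and would then "complete a mediation analysis of the association between EI engagement at 3 months and Bayley language and cognitive T scores, mediated by EI referral completion".
- The second takes program participation as the exposure. It tests "the association between referral completion (mediator) and program participation". Its final mediation model is written with program duration as the exposure, a term the SAP does not define, and referral completion is again the only mediator.

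The Aim 2 definitions equate referral completion with MDE completion. They also define the date of first EI service and the duration of EI services, but no Aim 2 analysis uses either. No visit-count variable is defined.

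The protocol treats services as something separate from the evaluation. Section 3.1.1 lists eligibility, initiation (IFSP) and number of service visits after the MDE, and section 6.4.2.1 plans an arm comparison of "dosage (duration of EI service use and number of EI service visits") among eligible children. Section 7.1.1 has the navigator give "ongoing assistance to overcome barriers to completing EI referrals and maintaining EI enrollment". The power model in section 6.5 assumes that "the sole impact of the intervention was on increasing enrollment into EI".

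**The concern.** A team that follows the SAP exactly will leave half of Hypothesis 2b untested. It can say whether completing the evaluation carries the effect on Bayley scores, but not whether receiving services does.

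The two differ because a child can complete the MDE, be found ineligible or never start, and receive nothing. The navigator also works after the evaluation, and Hypothesis 1b predicts that intervention children who are eligible will start services more often and stay longer. If so, some of the benefit reaches the child through EI without passing through the one mediator in the model. In the program-participation analysis that part would fall into the direct effect.

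The SAP's significance rule adds to this. Mediation is modelled only if arm is associated with both Bayley score and MDE completion. If navigation acts mainly after the MDE, the second condition may fail and no mediation result would be produced.

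**Working it through.** **Coverage.** I looked for any analysis linking EI services to Bayley scores.

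| Place | What is analysed | Services or dosage as mediator? |
|---|---|---|
| SAP 2b, first analysis | engagement → MDE → Bayley | No |
| SAP 2b, second analysis | program participation/duration → MDE → Bayley | No |
| SAP 2a | arm → engagement → referral completion | No; duration also missing as an outcome |
| SAP 1b | arm → initiation, arm → duration | No; arm-to-service leg only |
| Protocol 6.4.2.1 | arm → duration and visits, among eligible children | No; same leg |
| Protocol 6.4.2.2 | engagement as mediator of study outcomes | No |

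**The plan's own figure.** No figure is given for Hypothesis 2b. The related one is the 3-point effect in section 6.5, a gain of 10 points from EI enrolment at 50% versus 80%: 10 × (0.80 − 0.50) = 3.0. It reproduces, and it rests on enrolment yes/no, not on dose.

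**Illustration.** Let m be the share completing the MDE, q the share of completers who start EI, and 10 points the gain from starting, with no other pathway and arm as the exposure. I assume m₀ = 0.5 and m₁ = 0.8 (the enrolment rates of section 6.5, borrowed for MDE completion) and q₀ = 0.6. The documents give no separate values for m and q.

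- Total effect = 10 × (m₁q₁ − m₀q₀)
- Indirect effect via MDE = 10 × q × (m₁ − m₀), with q = q₀ or q₁ (the two standard decompositions)
- Remainder, labelled direct = total − indirect

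| q₀ → q₁ | Total | Indirect via MDE | Labelled direct | Share of total |
|---|---|---|---|---|
| 0.6 → 0.6 | 10 × (0.48 − 0.30) = 1.8 | 1.8 | 0 | 0% |
| 0.6 → 0.7 | 10 × (0.56 − 0.30) = 2.6 | 1.8 or 2.1 | 0.8 or 0.5 | 31% or 19% |
| 0.6 → 0.8 | 10 × (0.64 − 0.30) = 3.4 | 1.8 or 2.4 | 1.6 or 1.0 | 47% or 29% |

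In every row the whole effect truly acts through EI services.

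**Second check.** I held overall enrolment at 50% and 80%, so the total stays at 3 points, and varied how much of the difference arises before the MDE. In a large-sample regression adjusting for MDE alone, the direct share was 0% (MDE 50% → 80%), 27% (60% → 85%), 60% (70% → 85%) and 100% (85% in both arms, where the significance rule would probably stop the analysis). Adding service receipt brought it to 0% in every case.

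**Which added mediator works.** I simulated the table's scenarios with visits among starters assumed uniform on 1–40.

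- MDE plus visit count still leaves about 13% (0.6 → 0.7) and 22% (0.6 → 0.8) as direct.
- If starts are equal at 60% but intervention starters have 1–50 visits, MDE alone gives 0%, while adding visits creates a false direct effect of about −26%.
- MDE plus initiation leaves 0% in all of these cases, with or without visits added.

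In this model the benefit comes from starting, as in section 6.5, so initiation has to be in the model before dosage.

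**The case against.** The strongest reply is that this is a gap in a secondary aim and that its consequence is conditional. Several parts of that stand.

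- A reader might infer that dosage is *the* mediator of 2b and that the trial depends on a dose pathway. The SAP names dosage as one of two mediators and analyses the other. Section 6.5 assumes a yes/no enrolment effect and no dose response.
- A reader might infer that the service effect *would* appear as a non-EI effect. It only could. Misattribution needs a difference between arms in services among MDE completers, and it concerns only the program-participation analysis. Section 1.5 gives 50% for completed referrals and section 6.5 gives 50% for control enrolment. If these are meant as the same event, MDE mediation misattributes nothing.
- A reader might infer that services go unexamined. Hypothesis 1b and protocol section 6.4.2.1 compare initiation, duration or visits by arm, so a difference after the MDE could be seen. The SAP also does not say that a direct effect will be read as acting outside EI.
- For 2a, protocol section 6.4.2.2 plans engagement as a mediator of the study outcomes, which include completing EI services. That covers part of the gap, though not duration and not in the SAP.

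None of this supplies the missing analysis. The arm comparisons give one leg of the pathway. Nothing planned links services to Bayley scores or estimates an indirect effect through them.

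**Conclusion.** The mismatch is certain from the text: 2b hypothesises mediation by participation in EI services, and no analysis in either document tests it. The SAP analysis for 2a likewise omits its duration outcome.

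The consequence is a risk of unknown size. With arm as the exposure, the share of a service-mediated effect reported as direct is 0% when services after the MDE do not differ by arm and about 19% to 47% in the two assumed scenarios where they do. Other assumed splits can push it higher. All these figures rest on assumed MDE and service-start rates and on section 6.5's 10-point gain. Hypothesis 1b's own prediction makes a difference after the MDE plausible. The point should be corrected, but it touches a secondary mediation aim and leaves the primary comparison unaffected.

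**What to change.** In 2b:

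1. Use randomised arm as the exposure in place of program duration.
2. Keep MDE completion as the earlier step and add EI service initiation (yes/no by 12 months) as a mediator after it. This is closest to the pathway assumed in section 6.5.
3. Add dosage (duration, number of visits, or both, set to zero for children never served) alongside initiation, never in its place, as a further mediator labelled exploratory. Define the visit count in the SAP.

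In 2a, add EI participation or duration as an outcome.

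If the team does not want these models, it should remove service participation from both hypotheses.

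The data are already planned: parents report initiation and visits, and the EI agency supplies service-use data. The cost is SAP wording and one or two extra secondary models.

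A limitation should be stated with the dosage model. The Bayley is given only at the final visit, so there is no baseline score. If children with greater delay receive more services, the dosage–outcome association is confounded by severity. Transfer to Preschool EI during follow-up may also shorten duration for older children.

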## 2 STUDY OBJECTIVES

Our long-term goal is to develop effective strategies to promote child development and reduce disparities. As such, we developed the Opening Doors to Early Intervention Program, a patient navigation intervention designed to facilitate follow through with EI referrals and services. The overall objective of this project is to rigorously study the effects of the patient navigation intervention (Opening Doors to Early Intervention Program) on the use of EI referrals and services and on child developmental outcomes among at-risk urban minority children. Our central hypothesis is that patient navigation can improve parent engagement and knowledge, enhance follow through with EI services, and improve developmental outcomes among these children. Preliminary findings support this hypothesis and suggest the intervention is feasible and potentially effective. Findings from this study can be disseminated to similar urban counties across the U.S. to inform EI strategies and address disparities in early child development. We propose to test our central hypothesis and thereby

accomplish our overall objective for this application by pursuing the following specific aims:

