#### ***6.4.2.2 Specific Aim 2***

We will assess whether family engagement is a mediator of intervention treatment effects. We will address this aim by focusing on the role of family engagement using the EI Engagement questionnaire at 3, 6, 9, and 12 months as a mediator of the effect of the intervention on the study outcomes. Family engagement will occur post randomization and thus can be considered as a potential mediator as opposed to being a confounder. The response models discussed previously will be modified to include the EI Engagement questionnaire overall and domain scores as potential mediators in separate models to evaluate its mediating role in the association of interest. The association between outcome measures and the intervention conditional on the covariate will be compared to the marginal association estimated by the first aim.

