ODEI Study Statistical Analyses Plan

Title: The Opening Doors to Early Intervention Study (ODEI)

NCT Number: NCT03625115

Document Date: July 3rd, 2024

ODEI Study Statistical Analyses Plan

Aim 1: To test the effectiveness of the Opening Doors to Early Intervention Program on EI service use and child developmental status among poor minority children residing in an urban community.

- a. *Hypothesis 1a:* A greater proportion of children who are randomized to the intervention will complete EI referrals than children in the control condition at 12 months.

Analysis: Chi square analysis on the difference in completion of MDE by study arm and logistic regression on the difference in MDE completion by arm, controlling for sex, age, and primary care site.

- b. *Hypothesis 1b:* Among children eligible for EI services, children randomized to the intervention will initiate EI services at a greater rate & receiving a longer duration of EI services than children in the control condition.

Analysis: Chi square test on the difference in EI service initiation by arm and logistic regression, controlled for sex, age, and primary care site. Survival analysis with a Kaplan-Meier curve of EI duration of services by arm.

- c. *Hypothesis 1c:* As a result, children who are randomized to the intervention will have more favorable developmental outcomes than children in the control condition at 12 months.

Analysis: Logistic regressions to determine the difference in cognitive and language BSID III scores by arm, controlling for sex, age, and primary care site.

Variable Definitions:

- Completion of EI Referrals: Completion of Multidisciplinary Evaluation (MDE)
- Initiating EI services: Date of first early intervention service
- Duration of EI services: The time between the EI service initiation and discharge from early intervention OR 12 months from randomization (if discharge date is unavailable)
- Developmental outcomes: Language and cognitive composite scores from BSID III assessment.

Aim 2: To assess whether parent engagement mediates the effects of the Opening Doors to Early Intervention Program.

- a. *Hypothesis 2a:* Parent engagement will mediate the association between program participation and completion of EI referrals and participation in EI services (duration).

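### The SAP's engagement-to-MDE-to-Bayley mediation pools both arms without an arm term or covariates, so it can show an indirect effect of engagement when there is none

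*SAP*

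**What the plan says.** SAP Aim 2 describes three mediation analyses.

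- **Hypothesis 2a:** arm is the exposure, engagement the mediator and referral completion the outcome. The plan is to "complete a mediation analysis of the association between study arm and completion of EI referrals, mediated by parent EI engagement". One of the two screening tests before it is "the association between EI parent engagement at 3 months (mediator) and EI referral completion".
- **Hypothesis 2b, first analysis:** "a mediation analysis of the association between EI engagement at 3 months and Bayley language and cognitive T scores, mediated by EI referral completion". The screening tests are engagement against Bayley, and "the association between MDE completion (mediator) and EI engagement at 3 months".
- **Hypothesis 2b, second analysis:** program participation (later called program duration) is the exposure, referral completion the mediator and Bayley the outcome.

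Each mediation runs only on the condition "If both associations are significant". No covariate is named anywhere in Aim 2, and arm is not named in the first 2b analysis. By contrast, the Aim 1 regressions are specified as "controlling for sex, age, and primary care site", and those in Aim 3 carry the same three terms plus the moderator.

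Protocol section 6.4.2.2 describes a different model, with engagement as mediator of the intervention's effect: "The response models discussed previously will be modified to include the EI Engagement questionnaire overall and domain scores as potential mediators". Those response models contain the intervention.

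**The concern.** The documents themselves make arm a cause of both engagement and referral completion. Protocol section 2 states: "Our central hypothesis is that patient navigation can improve parent engagement and knowledge". Protocol sections 1.5 and 7.1.1 give the navigator practical tasks, such as help when an appointment is missed, that can move a family through the referral steps whether or not engagement changes. Section 6.5 expects a large arm difference in enrolment and a Bayley gain from enrolment.

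If both arms are pooled without an arm term, intervention families have higher engagement and higher MDE completion for reasons that need not be connected. The analysis then credits the navigator's practical help to engagement.

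Engagement and MDE completion are also not randomised. Protocol section 1.1 reports that barriers to completing referrals were more common in families with lower health literacy, so family factors are plausible further common causes. Aim 2 is where the trial says how the program works, and that explanation is what is at risk.

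**Working it through.** **Inputs from the documents (Protocol 6.5).** Enrolment is 50% in control and 80% in intervention. Enrolment adds 10 Bayley cognitive points. Expected completers are 130 control and 170 intervention. The 50%/80% and 10-point figures are for EI enrolment; I use them as a proxy for MDE completion, for which the documents give no figures. The protocol's 3-point difference follows from them: 10 × (0.80 − 0.50) = 3.0. The documents give no figure for the mediation analysis itself.

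**Assumptions.** Arm shifts engagement by 0.3 to 0.8 SD (only the direction is stated). Residual Bayley SD is 1, 7 or 15. Tests are two-sided at 0.05. Engagement has no effect on MDE or Bayley, so the true indirect effect is zero.

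**Step 1: size of the spurious effect.** Let p = 170/300 = 0.567, so p(1 − p) = 0.2456. Let d be the arm shift in engagement, in within-arm SD. Without an arm term, the slope of MDE on engagement is

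p(1 − p) × d × 0.30 / [1 + p(1 − p) × d²].

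The indirect effect is this slope times 10:

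- d = 0.3: 0.0221 / 1.0221 = 0.0216, giving 0.22 points per SD of engagement
- d = 0.5: 0.0368 / 1.0614 = 0.0347, giving 0.35
- d = 0.8: 0.0589 / 1.1572 = 0.0509, giving 0.51

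Simulation at 0.5 and 0.8 SD gives 0.34–0.35 and 0.50–0.52. With arm in the models it gives about zero.

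**Step 2: how often the whole sequence declares mediation.** I ran 2,000 simulated trials per setting at 130/170. Mediation is declared when engagement–Bayley and engagement–MDE are both significant and MDE then predicts Bayley given engagement. Arm is the only common cause.

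| Arm shift in engagement | Model | SD 1 | SD 7 | SD 15 |
|---|---|---|---|---|
| 0 | as written | 4.0% | 1.6% | 0.4% |
| 0.5 SD | as written | 22.2% | 7.2% | 2.6% |
| 0.5 SD | arm added | 3.4% | 1.0% | 0.6% |
| 0.8 SD | as written | 47.2% | 17.1% | 5.8% |
| 0.8 SD | arm added | 4.0% | 0.7% | 0.4% |

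Separate runs over 0.3 to 0.8 SD gave 10–49%, 3–16% and 1–7% for the three SDs, which agrees within simulation error.

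**Step 3: adding a family factor (strengths assumed), arm shift 0.5 SD.** The moderate factor moves engagement by 0.2 SD, MDE by log-odds 0.4 and Bayley by 0.2 residual SD. The stronger one uses 0.3, 0.6 and 0.3.

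| Family factor | Model | SD 1 | SD 7 | SD 15 |
|---|---|---|---|---|
| moderate | as written | 43.6% | 23.2% | 14.2% |
| moderate | arm added | 8.5% | 2.8% | 2.2% |
| moderate | arm and factor added | 4.2% | 0.6% | 0.3% |
| stronger | as written | 68.4% | 56.0% | 41.8% |
| stronger | arm added | 25.2% | 19.0% | 13.6% |
| stronger | arm and factor added | 4.2% | 1.0% | 0.4% |

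Arm alone is not enough once family factors matter.

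**Step 4: Hypothesis 2a.** The unadjusted engagement–MDE screening test is significant in about 26% of null trials at a 0.5 SD shift. The mediation that follows has arm as exposure, so a standard outcome model contains arm. The full 2a sequence then declares mediation in only about 2–3% of trials at 0.3, 0.5 and 0.8 SD.

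**The case against.** Four points can be made for the plan.

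- **Scope.** A reader might infer that every Aim 2 mediation leaves out the arm. Only one of the three does: arm is the exposure in 2a, and program participation or duration is the exposure in the second 2b analysis. This objection stands.
- **Size.** A reader might take the roughly 26% rate for the single engagement–MDE test as the rate of false mediation claims. It is not, because both screening tests must pass first. Protocol section 1.1 equates 0.43–0.75 SD with about 8–12 points, which implies an SD of about 16 to 19 (12/0.75 = 16.0; 8/0.43 = 18.6). The SD 15 column is therefore nearest the documents, and with arm as the only common cause its rates are around or below 5%. This stands for the error rate. It does not remove the biased estimate in Step 1, which does not depend on the residual SD. Nor does it cover family confounding, where the SD 15 rates are 14.2% and 41.8%.
- **Silence.** The SAP does not exclude adjustment, and Protocol section 6.3 allows confounders to be added as needed. That section is framed around the treatment effect, however, and the SAP does list covariates for its Aim 1 and Aim 3 regressions. An analyst following Aim 2 as written would fit none.
- **Protocol departure.** A reader might infer that this analysis breaks Protocol section 6.4.2.2. That section covers engagement as mediator of the intervention, which 2a addresses. The engagement-to-MDE-to-Bayley analysis is an addition that the protocol section does not describe, so it is not a contradiction.

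**Conclusion.** The concern holds for the first 2b analysis. As written, it gives a spurious indirect effect of about 0.2 to 0.5 Bayley points per SD of engagement when engagement does nothing. This assumes that arm shifts engagement by 0.3 to 0.8 SD and that the protocol's enrolment figures serve for MDE. With arm in the models the spurious effect is about zero. False claims of mediation range from about 1–7% (SD 15) to 10–49% (SD 1) from arm alone, and are higher if family factors also confound. If arm does not move engagement and no family factor confounds, there is no inflation.

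For 2a and the second 2b analysis the point is narrower: the 2a engagement screening test is unadjusted, and no covariates are named for mediators that are not randomised. The documents do not support a larger claim there. Aim 2 is secondary and the primary comparison is unaffected, so this should be corrected but does not threaten the main result.

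**What to change.** - Add randomised arm to both screening tests and to the mediator and outcome models of the engagement-to-MDE-to-Bayley analysis, and to the engagement–MDE screening test in 2a.
- In all Aim 2 mediator and outcome models, adjust for sex, age, site, baseline engagement, maternal education, income, StimQ and SAHL. Two need a note. StimQ is validated from 5 months of age (Protocol 5.1.2.1) while enrolment has no lower age limit, so state how younger infants are handled. SAHL may be completed at a later visit, after randomisation (Protocol 4.1.1), so record when it was taken.
- Add a sensitivity analysis for unmeasured confounding between mediator and outcome.

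The cost is SAP wording, a few more model terms and slightly wider intervals. All the covariates are already planned, so no new data are needed.
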